This SAP should be read in conjunction with the study protocol and case report forms (CRF). This version of the plan has been developed using the protocol amendment 3 dated 25APR2019 and CRF dated 15-Apr-2019. Any further changes to the protocol or CRF may necessitate updates to the SAP.

The study is an open-label study, investigators and subjects are not blinded. However, to avoid the introduction of operational bias into final study results and to increase the interpretability and reliability of the data, certain roles of the Sponsor and study team will be blinded. Details will be provided in the Data Blinding and Documentation of Aggregate Data Dissemination Plan. A final version of the SAP will be issued for sponsor approval prior to database lock, at which point the blinded team members will become unblinded to the actual randomization codes in aggregate form.

3.1 Changes from Protocol

Per FDA comment, Wald method has been replaced with logistic regression approach to calculate the difference in proportions along with the corresponding 90% CI for the primary endpoint and corresponding sensitivity analyses. The delta method will be used to calculate the standard error for the difference and the associated confidence interval.

Also, per FDA suggestion, separately in each treatment group, the imputation will use outcomes in patients who discontinued treatment but provided a visit Week 26 glycosylated hemoglobin (HbA1c) measurement if sufficient data are available to impute outcomes in patients without actual visit Week 26 recorded results, under the assumption of missing not at random (MNAR). Full details are provided in Section 11.7 below.

4. Study Objectives

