
Categorical variables will be summarized using counts and percentages. Continuous variables will be summarized using the number of observations, mean, standard deviation, median, minimum and maximum.

The secondary immunogenicity variables of the percentage of subjects with negative AIA at baseline who develop confirmed positive AIA up to visit Week 26 and the percentage of subjects with confirmed positive AIA after baseline and up to visit Week 26 will be compared between treatment groups using a normal test of difference in proportions. The difference in proportions will be estimated along with the corresponding 90% CI using Wald method for risk difference without continuity correction. The secondary immunogenicity variables of the percentage of subjects in each treatment group with confirmed positive AIA at baseline and

at least a 4-fold increase in titers after baseline and up to visit Week 26 and the percentage of subjects with confirmed positive AIA after baseline and up to visit Week 26 who develop any anti-insulin neutralizing antibodies after baseline and up to visit Week 26, will be compared between treatment groups using an exact test of difference in proportions. The difference in proportions will be estimated along with the corresponding 90% CI in the Safety Analysis Set. The exact confidence limits are computed by inverting 2 separate one-sided exact tests that are based on the score statistic. The mean change from baseline in each treatment group in AIA titers after baseline and up to visit Week 26 will be tabulated descriptively.

Safety variables will be summarized descriptively in the Safety Analysis Set consisting of all randomized subjects according to actual treatment received. All reported adverse events will be assigned a system organ class and preferred term according to the Medical Dictionary for Regulatory Activities and graded according to Common Toxicity Criteria for Adverse Events version 4.03. The number and percentage of subjects with adverse events (all adverse events, hypoglycemia, serious adverse events [including fatal], adverse events leading to termination of study treatment and/or early withdrawal from the study, IP-related adverse events, and injection site reactions) will be presented. Vital signs, body weight and BMI, ECG, and laboratory results will be summarized by treatment and visit.

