#### **12.9.1.2 Subjects with a 4-fold Increase in Titers**

The percentage of subjects in each treatment group with confirmed positive AIA at baseline who have at least a 4-fold increase in titers after baseline and up to visit Week 26 will be compared using an exact test of difference in proportions.

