11.6.2 Secondary Immunogenicity Endpoints

All analyses will include on and after study treatment AIA data up to visit Week 26.

11.6.2.1 Subjects with Negative Anti-Insulin Antibodies at Baseline Who Develop Newly Confirmed Positive Anti-Insulin Antibodies

The percentage of subjects in each treatment group with negative AIA at baseline who develop newly confirmed positive AIA after baseline and up to visit Week 26 will be summarized in proportions. The difference in proportions will be estimated along with the corresponding 90% CI in the subset of SS using a logistic regression model.

Missing data will be imputed as described for the primary endpoint in Table 4.

Sponsor: Gan & Lee Pharmaceuticals, USA Corporation
Protocol no: GL-GLAT2-3002

Statistical Analysis Plan
Version Date: 16-Nov-2020

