11.6.2.2 Subjects with Important Increase in AIA Titers

The percentage of subjects in each treatment group with confirmed positive AIA at baseline who develop important increase (at least a 4-fold increase) in titers (defined in Section 7.2) up to visit Week 26 will be compared using an difference in proportions. The difference in proportions will be estimated along with the corresponding 90% CI in the subset of SS (with positive AIA at baseline) using a logistic regression model with treatment as the only independent variable in the model.

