11.6.2.3 Change in Anti-Insulin Antibody Titer

The change from baseline in AIA titers at visit Week 12 and visit Week 26 will be summarized descriptively in subjects with confirmed positive AIA at baseline. Though not specified in the protocol, this analysis is planned for the subset of subjects with confirmed positive AIA only.

11.6.2.4 Subjects with Confirmed Positive Anti-Insulin Antibodies Who Develop Newly Confirmed Neutralizing AIA

The percentage of subjects in each treatment group with confirmed neutralizing AIA after baseline and up to visit Week 26 will be compared using difference in proportions. The difference in proportions will be estimated along with the corresponding 90% CI in the SS using a logistic regression model with treatment as the only independent variable in the model.

Missing data will not be imputed, the percentages will be based on the subjects with documented confirmed positive AIA after baseline and up to visit Week 26.

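### For two secondary immunogenicity endpoints the SAP replaces the protocol's exact 90% confidence interval with a treatment-only logistic model, and SAP 3.1 neither lists nor justifies the change

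*SAP*

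**What the plan says.** The protocol divides its four tested secondary immunogenicity proportions by method (synopsis, Statistical Methods).

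- **Normal test.** Newly positive AIA in baseline negatives, and any confirmed positive AIA after baseline, get a normal test with the "corresponding 90% CI using Wald method for risk difference without continuity correction".
- **Exact test.** The 4-fold titer rise in baseline positives, and neutralizing antibodies in confirmed positives, get an exact test with a 90% interval: "The exact confidence limits are computed by inverting 2 separate one-sided exact tests that are based on the score statistic". Protocol 12.9.1.2 repeats that the titer endpoint "will be compared using an exact test of difference in proportions", and 12.9.1.4 says the same for neutralizing antibodies.

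The SAP applies logistic regression to all four. For the titer endpoint, 11.6.2.2 estimates the difference and its 90% CI "in the subset of SS (with positive AIA at baseline) using a logistic regression model with treatment as the only independent variable". For neutralizing antibodies, 11.6.2.4 gives the "90% CI in the SS using a logistic regression model with treatment as the only independent variable in the model", then adds that "the percentages will be based on the subjects with documented confirmed positive AIA after baseline and up to visit Week 26".

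SAP 3.1 lists the changes from the protocol. On this subject it has one entry: following an FDA comment, Wald is replaced by a "logistic regression approach to calculate the difference in proportions along with the corresponding 90% CI for the primary endpoint and corresponding sensitivity analyses", with delta-method standard errors.

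**The concern.** The protocol kept an exact method for the two comparisons that are restricted to antibody-positive subsets. The SAP drops it, and the reason given in 3.1 cannot cover the change: that entry concerns the primary endpoint and its sensitivity analyses, and it replaces Wald, which was never the protocol's method here. A reader who relies on 3.1 would not learn that these intervals had changed in kind.

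Both endpoints are planned between-arm comparisons in a trial whose primary objective is immunogenicity equivalence. If a subset is small and events are rare, the reported intervals could look more precise than the data allow, or could fail to be produced at all.

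**Working it through.** **1. Which interval the SAP model gives.** In a treatment-only logistic model, the log-odds in an arm with *n* subjects and proportion *p* has estimated variance 1/[n·p(1−p)]. The derivative of *p* with respect to the log-odds is p(1−p). The delta method therefore gives each proportion a variance of [p(1−p)]² / [n·p(1−p)] = p(1−p)/n. Summed over the arms, this is the unpooled Wald variance. Numerically, 95/275 vs 80/275 gives a difference of 0.05455 and a standard error of 0.03965 by both routes.

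The delta method is named in SAP 3.1 and 11.6.1.1 for the primary analysis. Sections 11.6.2.2 and 11.6.2.4 name no CI construction, so carrying it over is an inference. No other risk-difference method is offered for these endpoints.

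**2. Zero counts.** With no events in one arm, that arm's log-odds, and so the logistic treatment estimate, is not finite. With no events in either arm, the Wald interval has zero width. At assumed true rates of 5% and 2% with 30 per arm, the chance of an empty arm is 0.95^30 = 0.2146 and 0.98^30 = 0.5455. Hence:

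- both arms empty: 0.2146 × 0.5455 = 11.7%
- at least one arm empty: 1 − 0.7854 × 0.4545 = 64%

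The chance of at least one empty arm is 33% at 60 per arm and 20% at 83. The figure 83 is 275 × 30%, rounded up, and borrows the planning example's 30% rate only as an illustration.

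**3. Coverage of the nominal 90% Wald interval.** This was found by full binomial enumeration. The plan gives no subset size or rate for either endpoint, so every input here is an assumption.

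| Per arm | Assumed true rates | Coverage |
|---|---|---|
| 15 | 5% vs 2% | 61.5% |
| 15 | 10% vs 5% | 76.5% |
| 20 | 5% vs 2% | 72.8% |
| 20 | 10% vs 5% | 82.1% |
| 30 | 5% vs 2% | 75.0% |
| 40 | 4% vs 2% | 76.7% |
| 60 | 2% vs 1% | 78.2% |

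Over nine rate pairs from 2% vs 2% to 30% vs 30%, coverage is 87.9–92.4% at 60 per arm and 88.3–89.6% at 83. The exact interval covers at least 90.1% for all nine pairs at 15, 20, 30, 60 and 83 per arm.

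**4. Example 90% intervals for the difference.**

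| Events | Wald | Exact |
|---|---|---|
| 0/30 vs 0/30 | (0, 0) | (−9.5%, 9.5%) |
| 0/30 vs 2/30 | (−14.2%, 0.8%) | (−19.5%, 2.9%) |
| 4/83 vs 2/83 | (−2.3%, 7.2%) | (−2.9%, 8.5%) |

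The first exact limit can be checked by hand: 1 − 0.05^(1/30) = 9.5%.

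**5. What is not affected.** The planned power at a 30% rate and 12% margin is 2Φ(0.12/√(2 × 0.3 × 0.7/275) − 1.645) − 1 = 84.6%, against the stated 85% or so. It concerns the primary endpoint only. SAP 11.6.1.4 places only primary immunogenicity and efficacy in the testing order.

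**The case against.** The best case for the SAP is that little depends on this. The two endpoints have no margin and no place in the hierarchy, and the subsets may turn out large enough for Wald to be adequate. About 83 post-baseline positives per arm would give near-nominal coverage for all nine pairs in the grid. The exact interval is also markedly conservative where it is most needed: at 15 per arm it covers 96.4–100% for the five pairs with both rates at or below 10%. A sponsor could instead declare the logistic method and add a zero-event rule. All of this stands and limits the severity. It does not explain why 3.1 is silent.

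Four stronger readings are tempting, and the documents do not support them.

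- **That the equivalence conclusion is at risk.** No equivalence decision uses these endpoints.
- **That undercoverage is certain.** Excluding subjects with previously documented anti-insulin antibodies (exclusion 10) makes a small baseline-positive subset plausible, but no size is given.
- **That the shortfall stops at about 30 per arm.** The 40 and 60 per arm rows in the table show otherwise when rates are very low and unequal.
- **That the primary model is wrong because it omits baseline AIA status.** Neither document promises covariate adjustment, and the model was adopted after an FDA comment. A covariate chosen after last follow-up (13 August 2019) in an open-label trial would be a debatable trade-off for a gain that depends on assumed prognostic strength.

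**Conclusion.** The point holds as an undeclared and unjustified departure from the protocol's exact method in SAP 11.6.2.2 and 11.6.2.4. The textual contradiction needs no assumption. The numerical consequence needs two: that the delta method carries over to these sections, and that at least one subset is small or has rare events. Under those assumptions the nominal 90% interval can cover as little as 61.5% in the cases tabulated. It can also have zero width, or rest on a non-finite logistic estimate, with no stated fallback. With 60 or more per arm and rates that are not very low, the difference is minor. The change should be corrected, but it does not threaten the primary result.

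**What to change.** Before database lock:

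1. In SAP 11.6.2.2 and 11.6.2.4, restore the protocol's exact test and exact score-based 90% interval. This also settles the zero-event cases.
2. In 11.6.2.4, state that the CI uses the same confirmed-positive denominator as the percentages. The section now refers both to the full safety set and to the positive subset.
3. In 3.1, list the other unlisted moves to logistic regression: 11.6.2.1 ("90% CI in the subset of SS using a logistic regression model"), 11.6.2.5 and 11.7.2.1. The protocol used a Wald interval for the first two and a normal approximation for the third (protocol 12.9.3.1). These moves are numerically neutral under the delta method with treatment as the only term. Section 11.6.2.5 says that it is; 11.6.2.1 and 11.7.2.1 should say so too.

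The cost is SAP wording and an exact risk-difference call for two tables. Intervals become wider and conservative: total width is 11.4 instead of 9.5 percentage points at 4/83 vs 2/83, and 26.4 instead of 21.0 at 3/30 vs 1/30.

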4.1 Primary Study Objective

- To evaluate equivalence of Gan & Lee Insulin Glargine Injection and Lantus® in terms of immunogenicity by comparing the proportions of subjects between the two treatment arms who develop treatment induced anti-insulin antibodies (AIAs), which is defined as either treatment emergent AIA development or important increase (at least 4-fold) in AIA titers up to visit Week 26.

4.2 Secondary Study Objectives

4.2.1 Immunogenicity

- To evaluate the percentage of subjects with negative anti-insulin antibodies (AIAs) at baseline who develop confirmed positive AIA up to visit Week 26, the percentage of subjects with at least a 4-fold increase in titers compared to baseline value, mean change from baseline in AIA titers between treatment groups, the percentage of subjects with confirmed positive AIA who develop any anti-insulin neutralizing antibodies up to visit Week 26, and percentage of subjects who develop confirmed positive AIA up to visit Week 26 of Gan & Lee Insulin Glargine Injection in comparison with that of Lantus®

4.2.2 Safety

- To evaluate the safety of Gan & Lee Insulin Glargine Injection in comparison with that of Lantus®

4.2.3 Efficacy

- To evaluate the efficacy of Gan & Lee Insulin Glargine Injection in comparison with that of Lantus® by comparing subjects' average change from baseline of HbA1c at visit Week 26 between the two treatment arms. This secondary efficacy objective is not specified in the protocol objectives as a key secondary objective, however it is specified as a key secondary endpoint, and the evaluation of the efficacy measured by change from baseline of HbA1c at visit Week 26 of Gan & Lee Insulin Glargine Injection in comparison with that of Lantus® will undergo statistical analysis as a key secondary endpoint of the study.
- To evaluate the percentage of subjects who achieve a fasting blood glucose (FBG) test result of ≤ 8.0 mmol/L (≤ 144.0 mg/dL) at visit Week 26, the percentage of subjects who achieve a HbA1c of $< 7.0\%$ at visit Week 26 of Gan & Lee Insulin Glargine Injection in comparison with that of Lantus®

4.3 Exploratory Objective

- To investigate the retrospective hypoglycemic rate and time in hypoglycemia and hyperglycemia using continuous glucose monitoring (CGM) data

5. Study Design

This open-label, randomized, multicenter study is designed to compare the immunogenicity, efficacy, and safety of Gan & Lee Insulin Glargine Injection compared with that of Lantus® in subjects with Type 2 diabetes mellitus to determine equivalence.

Subjects between the ages of 18 and 75 who meet the study inclusion criteria and none of the exclusion criteria as defined in the protocol, will be centrally randomly assigned in a 1:1 allocation ratio to receive either Gan & Lee Insulin Glargine Injection or Lantus®. Randomization and the level of blinding in this study are further described in Section 5.2. Subjects will participate for 2 weeks' screening + 26 week treatment + 4 week following up in total a maximum of 32 weeks in the study. Recruitment will stop when approximately 275 subjects have been randomly assigned to each treatment group. The study will end when the last subject completes the end-of-study visit, or discontinues the study treatment, whichever occurs first.

During the 2 weeks between screening and randomization, once subjects already on basal insulin are determined eligible for the study, they will have their insulin dosing optimized according to Table 1. They will also have any appropriate adjustments in their other antidiabetes medication (OAM) dosing that may

be required because of the optimization of their insulin dosing. Subjects who are insulin-naïve will have their OAM dosing optimized to prepare them for starting basal insulin therapy.

Table 1: Basal Insulin Dose Adjustment Based on Fasting Glucose Result between Screening and Randomization

Lowest Average Fasting Plasma Glucose (Pre-Breakfast) Value for 3 Days	Adjust Basal Insulin Dose (Units per Dose)
> 271 mg/dL (> 15.1 mmol/L)	+ 6 U
181 – 270 mg/dL (> 10.1 – 15.0 mmol/L)	+ 4 U
151 – 180 mg/dL (> 8.4 – 10.0 mmol/L)	+ 2 U
131 – 150 mg/dL (> 7.3 – 8.3 mmol/L)	+ 1 U
71 – 130 mg/dL (> 3.9 – 7.2 mmol/L) (Target Level)	Maintain Current Dose
56 – 70 mg/dL (3.1 – 3.9 mmol/L)	- 2 U
< 56 mg/dL (< 3.1 mmol/L)	- 4 U

At the screening visit, the subject will have an Abbott FreeStyle Libre Pro Flash Glucose Monitoring sensor applied to the back of the upper arm to record the interstitial glucose concentration every 15 minutes for 8 days. At the randomization visit (Visit 2), subjects will receive supply of insulin pens with Investigational Product (IP) and the Investigator or designee will train subjects on all study procedures and proper dose administration.

[figure not shown]
Subjects in both treatment groups will be assessed every 2 weeks after Visit 2 (randomization visit) through Week 22 (these assessments will be done either through in person clinical visit or will be done through a telephone call) and then at Week 26; they will attend 9 clinic visits (the screening visit, the randomization visit (Day 1, see Section 7.1), and at Weeks 2, 4, 8, 12, 16, 20, and 26), 2 brief visits with no study assessments during which a CGM sensor will be applied (8-10 days before the visits at Weeks 12 and 26 for subjects to wear for a 8-day period), and they will be contacted by telephone at Weeks 6, 10, 14, 18, and 22. The Week 26 visit (Visit 9) will be the end-of-treatment (EOT) visit (see Section 7.1). See Figure 1 for summary of study visits. All study procedures and assessments (see Table 2) are described in more detail in Section 8.1 in the study protocol.

Sponsor: Gan & Lee Pharmaceuticals, USA Corporation
 Protocol no: GL-GLAT2-3002

Statistical Analysis Plan
 Version Date: 16-Nov-2020

Figure 1: Study Diagram

d = day; EOT = End of Treatment; ET = Early Termination; FU = Follow-up; TC = telephone call; V = visit; W = week

Note: At weeks 11 and 25, subjects will attend a brief visit for application of a continuous glucose-monitoring sensor.

Sponsor: Gan & Lee Pharmaceuticals, USA Corporation
Protocol no: GL-GLAT2-3002

Statistical Analysis Plan
Version Date: 16-Nov-2020

5.1 Sample Size and Power

Enrollment was planned for 550 subjects overall (275 subjects per treatment group). The primary analysis for immunogenicity primary endpoint was to be an equivalence test for the difference in proportion of subjects who develop treatment-induced AIAs between Gan & Lee insulin Glargine Injection and Lantus® using the 2 Wald one-sided tests (TOST) approach with $\alpha=0.05$ (Chow and Shao 2002 (1)). After scientific and regulatory review, the method to evaluate immunogenicity equivalence will be the 90% confidence intervals of risk difference from logistic regression analysis (see Section 3.1). Under this newly adopted approach, no power loss is expected.

This sample size of 275 subjects per treatment group was chosen to achieve over 80% power using the TOST equivalence test for two proportions, a risk difference of zero and equivalence margins dependent on the observed treatment-induced AIA rate per Table 3 below. For example, a sample size of 550 will provide approximately 85% power for the TOST equivalence test using a treatment-induced AIA rate of 30% and a margin of 12% (See Table 3). The treatment-induced AIA is defined as newly confirmed positive AIA development or important (at least a 4-fold) increase in AIA titers, after baseline and up to visit Week 26 (see the definition of Primary Endpoint in Section 6.1 and Section 7.2). No drop outs are considered in the calculation. A larger than expected early discontinuation rate was observed as part of study monitoring activities and therefore protocol amendment 3 approved on 25-Apr-2019 included procedures to encourage subjects to return for assessments even if they have discontinued treatment early.

The appropriate similarity margin, based on the actual observed event rate for the intended reference product, will be used for final analysis after database lock as summarized in the Table 3 below. The power calculation in the table was adapted for a sample size of 550 using the treatment-induced AIA rate for the reference product. Linear interpolation will be used for values between AIA rates in the table.

Sponsor: Gan & Lee Pharmaceuticals, USA Corporation
Protocol no: GL-GLAT2-3002

Statistical Analysis Plan
Version Date: 16-Nov-2020

Table 3: Similarity margins for actual observed event rate of proposed biosimilar to insulin glargine for various immunogenicity event rates

Treatment-induced AIA Rate for the Reference Product	Margin	Power
10%	7.9%	83%
15%	9.3%	83%
20%	10.5%	84%
25%	11.3%	84%
30%	12.0%	85%
35%	12.5%	85%
40%	12.8%	85%
45%	13.0%	85%
50%	13.1%	85%
55%	13.0%	85%
60%	12.8%	85%
65%	12.5%	85%
70%	12.0%	85%
75%	11.3%	84%
80%	10.5%	84%
85%	9.3%	83%
90%	7.9%	83%

Sample size calculations were performed using EAST Version 6.4 (East 6 (2020) (2)).

